#### 20.1 Database lock

After written recording, each research worker will transcribe data onto the eCRF within one working week of a participant assessment. After completion of all follow-ups and prompt entry of data, the Trial Manager will review the data and issue queries. The research worker must then answer these queries before the participant's data is 'frozen' within the database. After that time, changes will not be made to the database by the centres unless specifically requested by the Study Office in response to statistician data checks. At the end of the trial, the centre PI will review all the data for each participant and provide electronic sign-off to verify that all the data are complete and correct. At this point, all data will be formally locked for analysis. At the end of the trial, each centre will be supplied with a CD-ROM containing the eCRF data for their centre. This will be filed locally for any future regulatory or internal audit.

## 21. Publication Policy

A layered communication plan for the lifecycle of the trial will be developed to communicate material in the best format to our audiences (including service users; family members; policy makers; treatment commissioners; the general public; and scientific peers). We will: (i) report quarterly on progress to each of the three clinics' Service User Forums; (ii) produce an annual trial newsletter (MHRN to disseminate); (iii) seek to describe our work at MHRN hub conferences; (iv) seek MHRN support for a conference in the last quarter of the study as part of our dissemination work; and (v) produce results and practice briefings for Public Health England and national stakeholder audiences. This collective activity will support the communication of results via general medical journals.

## 22. Insurance / Indemnity

Insurance for claims relating to the study design and co-ordination will be provided by KCL. NHS indemnity for study sites will be available.

# 23. Financial Aspects

Funding to conduct the trial is provided by the National Institute for Health Research Health Technology Assessment program.

### 24. Time Table

The NEAT Trial will be completed over 45 months. The study will start in September 2014 and first patient will be enrolled in November 2015. The study will end in May 2018. In each of the two clinical recruitment centres, 1 participant will be recruited each week with recruitment of the 300 participants completed in 104 weeks.

There will be four phases: preparation, participant recruitment, and analysis, as follows.

NEAT phase	Activity	Study month	Start date	End date
1	Preparation	1-11	09/14	08/15
II	Recruitment	12-32	09/15	04/17
III	Follow-ups	15-40	12/15	12/17
IV	Analysis and final reporting	41-45	01/18	05/18

The project timetable and milestones are summarised as follows:

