# 1. Study Synopsis

Title Of Clinical Trial:	A randomised controlled trial of the clinical and cost-effectiveness of extended-release naltrexone and oral naltrexone
Protocol Short Title/ Acronym:	Naltrexone Enhanced Addiction Treatment trial (NEAT)
Study Phase If Not Mentioned In Title:	Phase III clinical trial of an investigational medicinal product
Purpose Of Clinical Trial:	The NEAT trial is for adults with a diagnosis of opioid use disorder (DSM5) in the past year, who are now detoxified (zero opioid tolerance) and want help to stay away from heroin. The primary purpose of the trial is to evaluate the clinical and cost-effectiveness of enhanced naltrexone (NTX) relapse prevention therapy programme for the treatment of opioid use disorder (following NICE, 2007). The NEAT trial will evaluate two formulations of this medication: a 90-day implanted, long-acting form (XR-NTX; 'iGen/Atral-Cipan' device herein), and a short-acting oral tablet form (O-NTX, the active comparator).
	A. Is XR-NTX treatment more effective than placebo at reducing heroin use?
	B. Is XR-NTX more effective than O-NTX at reducing heroin use?
Primary Objective:	C. Is XR-NTX more cost- effective than placebo in terms of quality-adjusted life years?
	D. Is XR-NTX more cost-effective than O-NTX in terms of quality-adjusted life year?
	A. To compare treatment retention and medication and psychological intervention adherence rates among the XR-NTX, O-NTX and placebo conditions.
	B. To contrast the XR-NTX, O-NTX and placebo conditions on quality of life indices.
	C. To contrast XR-NTX, O-NTX and placebo conditions on:
	heroin and cocaine craving;
	
 
self-reported opioid, cocaine, amphetamine and benzodiazepine use (with past 48 hour abstinence verified via urine drug screening [UDS]);
 

Secondary Objectives:	alcohol use;
	injection health risk behaviours;
	
 
psychological health (depression and anxiety symptoms);
 

	molecular (genetic) biomarkers of treatment response.
	
 
Plasma naltrexone and 6-β-naltrexol (the primary metabolite of NTX);
 

	D. To document the safety of XR-NTX and O-NTX.
	E. To compare patterns of heroin relapse among the XR-NTX, O-NTX and placebo conditions
Trial Design:	A three-year definitive, three-centre, three-arm, parallel group, placebo controlled, double-blind, double-dummy, randomised clinical trial, with primary outcomes assessed 12 weeks after randomisation, and with clinic

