## 12.2 Estimated required sample size

With an anticipated 0.8 effect size, a common standard deviation of 30, expected attrition at 40%, and testing significance at 2.5%, a sample size of 300 participants randomized on a 1:1:1 basis to the three arms (100 participants in each arm) will have 98% power to detect a 25 point difference in the percentage heroin-negative urines for the planned comparisons of active treatment arm XR-NTX vs. placebo and active treatment arm XR-NTX vs. standard oral treatment O-NTX.

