## Contract start date 1st September 2014 (45 months total duration)

August 2014	CTA application to MHRA with Manufacturer's IB and IMP dossier	
5.1	List Too/DMo	
February 2015	Joint TSC/DMC meeting	
April 2015	Employ trial manager	
August 2015	Seek all R&D approvals	
	Place IMP purchase and placebo manufacture orders	
	Prepare study specific process documents	
	Test and signoff eCRF system	
	Study site staff training	
September 2015	Conduct site initiation visits at all sites	
	IMP delivery to all sites	
	First patient enrolled	
February 2016	Annual progress report to DMC, NIHR and MHRA	
July 2016	DMC and TSC meetings	
	Annual safety report to MHRA	
	Annual progress report to ethics	
January 2017	DMC and TSC meetings	
February 2017	Annual progress report to DMC, NIHR and MHRA	
April 2017	All sites end recruitment	
July 2017	DMC and TSC meetings	
	Annual safety report to MHRA	
	Annual progress report to ethics	
December 2017	Field-work (follow up) completed	
January 2018	Site close out visits	
	Database lock	
	Primary analysis begins	

May 2018	Analysis complete	
	HTA report submitted	
	Primary paper submitted for publication	

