### 25.2 Objectives

- To understand factors (patient, contextual and intervention related) that both facilitated and impeded the screening process of the NEAT trial
- To understand factors (patient, contextual and intervention related) that encouraged or discouraged patients from agreeing to participate in the NEAT trial
- To understand factors (patient, contextual and intervention related) that both facilitated and impeded progression from agreement to participate in the NEAT trial to actually joining the trial
- 4. To assess the treatment experiences of individuals who were accepted onto the NEAT trial but did not progress to join the trial

5. To assess the treatment experiences of all individuals who participated in the NEAT trial

- 6. To explore intended and unintended outcomes of participation in the NEAT trial
- 7. To ascertain the views and experiences of drug agency staff and research team members about the design and conduct of the NEAT trial
- 8. To ascertain the views of drug agency staff and research team members about how a future naltrexone trial should be designed and conducted
- 9. To assess whether the problems encountered were likely to be specific to naltrexone
- 10. To assess whether the problems encountered were likely to be specific to addiction trials

This follow-up has been designed to be incorporated into the NEAT trial over the period when it is being wound down. As a result, it is subject to a number of constraints. First, speed of data collection will be essential to ensuring that those involved in the NEAT trial can both be successfully located and recall sufficient information about the trial to enable meaningful analyses. Second, the small number of participants successfully recruited onto the trial (n=6) limits the scope of data collection. Third, time delays in securing NHS ethics approval could jeopardise the follow-up. For these practical reasons, it will be necessary to undertake a small exploratory follow-up study. Qualitative research, involving semi-structured interviews with a diverse range of individuals involved in the NEAT trial, provides an ideal method of generating the required data.

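### Section 24's accrual plan (two centres, one participant per week each, 104 weeks) yields 208 participants, not the stated 300, and fewer within the scheduled recruitment window

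*Protocol*

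**What the plan says.** Section 24 fixes the rate, the number of centres, the duration and the target in one sentence: in each of the "two clinical recruitment centres, 1 participant will be recruited each week with recruitment of the 300 participants completed in 104 weeks". The same section states that the "first patient will be enrolled in November 2015", while its phase table runs recruitment over study months 12-32, from 09/15 to 04/17. The milestone list under section 24 puts "First patient enrolled" in its September 2015 row and "All sites end recruitment" in its April 2017 row. The synopsis time line gives a third first-patient date, March 2015.

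The number of centres also varies. The synopsis describes "A three-year definitive, three-centre, three-arm, parallel group", and sections 15 and 21 also refer to three centres or clinics. The synopsis settings line and sections 4, 6.1, 7.3 and 24 say two.

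Section 12.2 states that "a sample size of 300 participants randomized on a 1:1:1 basis to the three arms (100 participants in each arm) will have 98% power". Section 25.2 of the same version, dated June 2017, notes that "the small number of participants successfully recruited onto the trial (n=6) limits the scope of data collection", and the introduction to section 25 dates the decision to wind down to November 2016.

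**The concern.** Sample size and power are headline design figures, and the recruitment plan is what makes them credible. Here the rate, the number of centres and the duration, multiplied together, do not give the target stated in the same sentence. The duration also does not fit the calendar printed beneath it. A funder or oversight committee that took the sentence at face value would believe that 300 was reachable at one participant per centre per week, when that rate falls about a third to a half short. Section 25 says the trial's lessons should inform later naltrexone trials, so the record of what the plan could deliver still matters after closure.

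**Working it through.** **Inputs.** Two centres, 1 participant per week in each, 104 weeks, target 300 (section 24). Recruitment 09/15 to 04/17, months 12-32, or first patient November 2015 (section 24). First patient March 2015 (synopsis). Difference 25 points, SD 30, effect size given as 0.8 (25/30 = 0.833), attrition 40% (section 12.1). Two-sided 2.5% per comparison (section 12.4). Allocation 1:1:1 (section 12.2).

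**Step 1: reproduce the stated power.** Analysed per arm: n = (300/3) x 0.6 = 60. For a two-sample t test the noncentrality is d x sqrt(n/2), with 2n - 2 degrees of freedom. For n = 60 it is 0.8 x sqrt(30) = 4.38, or 0.833 x sqrt(30) = 4.56. Power is 98.2% and 98.9% respectively. The 98% in section 12.2 is reproduced.

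**Step 2: accrual = centres x rate x weeks.** Windows run from the first day of the starting month to 30 April 2017.

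| Basis | Weeks | Two centres | Short of 300 |
|---|---|---|---|
| Section 24 sentence | 104 | 208 | 92 (31%) |
| Phase table and milestones, from Sept 2015 | 86.7 | 173 | 127 (42%) |
| Section 24 text, from Nov 2015 | 78.0 | 156 | 144 (48%) |
| Study months 12-32 read as 21 months | 91.3 | 183 | 117 (39%) |
| Synopsis, from March 2015 | 113.0 | 226 | 74 (25%) |

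Three centres over 104 weeks would give 3 x 104 = 312. Over section 24's own windows, three centres would give only 3 x 86.7 = 260 or 3 x 78 = 234.

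**Step 3: does 104 weeks fit the calendar?** From 1 September 2015 it ends on 29 August 2017. The last 36-week visit then falls in May 2018, after the December 2017 end of fieldwork and the January 2018 database lock. From 1 November 2015 the last visit falls in July 2018, after the stated study end of May 2018.

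**Step 4: what 300 requires.** Rate per centre per week = 300 / (2 x weeks): 1.44 over 104 weeks, 1.73 over 86.7 and 1.92 over 78. At one per centre per week it takes 300/2 = 150 weeks, which runs to July 2018 (September start) or September 2018 (November start). Both are past May 2018.

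**Step 5: power at the accrued sizes** (n per arm = N/3 x 0.6, method as in step 1).

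| N | n per arm | Power, d = 0.8 | Power, d = 0.833 |
|---|---|---|---|
| 208 | 41.6 | 91% | 93% |
| 173 | 34.6 | 85% | 88% |
| 156 | 31.2 | 80% | 84% |

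If everyone randomised were analysed with the same SD and effect (an assumption), power would be above 99% at 208, about 98-99% at 173 and about 96-97% at 156.

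**The case against.** The strongest reply is that section 12.2 contains no error. It says what 300 participants would give, and that is right. The required size follows from the effect, SD, alpha and attrition, and a faulty scheduling sentence does not alter it. This stands: the fault is in the accrual figures, and keeping 300 with a rate and window that produce it would be a full repair.

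It can also be said that the loss of power is moderate and depends on missing-data handling. Section 9.1 describes counting missed samples as positive, under which all randomised participants could be analysed. It also mentions multiple imputation, so the handling is not settled. The power figures are therefore conditional. The shortfall in numbers is not.

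The synopsis start of March 2015 would leave more than 104 weeks, so the duration is unavailable only on section 24's own dates. Even so, that start yields 226.

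Finally, the trial had been wound down before this version was written, so correction cannot change recruitment. That limits the practical effect but leaves the text inconsistent.

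Two stronger readings are tempting. A reader might infer that the sentence was simply left over from a three-centre design. The 312 and the surviving three-centre wording make that plausible, but the protocol does not say so, and three centres would still miss 300 in section 24's windows. A reader might also infer, from the six recruited, a specific collapse in power or a primary model with no residual degrees of freedom. The protocol does not support this: the arms of the six are not reported, section 9.1 names only a regression model, and how so few data are analysed belongs to the analysis plan.

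**Conclusion.** The accrual statement in section 24 is wrong as written. Two centres at one participant per week each give 208 in 104 weeks, 31% below 300. Section 24's start and end dates give 156 to 173, a shortfall of 42-48%. The other readings (183 and 226) also miss 300. The counts assume only the stated rate and calendar months taken from first to last day.

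As a result, the plan's own rate does not deliver the size on which the 98% rests. With 40% attrition, two-sided 2.5% and an effect size of 0.8 to 0.833, power falls to between 80% and 93% depending on the window. The documents do not support calling the power calculation itself wrong, or calling the planned trial badly underpowered for a 25-point difference: power stays at 80% or above in each scenario calculated.

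**What to change.** Settle on one number of centres, one first-patient date and one recruitment window, and carry them through the synopsis (design line and time line), sections 15 and 21, and section 24 with its phase table and milestones. Then correct the accrual sentence in one of two ways:

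- keep 300 and state the rate it requires: 1.44 per centre per week over 104 weeks, 1.73 over 87 or 1.92 over 78, with a window that leaves room for 36-week follow-up; or
- keep one per centre per week and state beside section 12.2 the size and power this delivers, for example 208 and about 91% at effect size 0.8 with 40% attrition.

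Since section 25 records closure with six recruited, mark 300 and 98% as planned figures that were not achieved.

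The cost is protocol wording only, with no added participants. The downside is that the stated size or power, or the rate asked of each centre, looks less favourable.

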## Contract start date 1st September 2014 (45 months total duration)

August 2014	CTA application to MHRA with Manufacturer's IB and IMP dossier	
5.1	List Too/DMo	
February 2015	Joint TSC/DMC meeting	
April 2015	Employ trial manager	
August 2015	Seek all R&D approvals	
	Place IMP purchase and placebo manufacture orders	
	Prepare study specific process documents	
	Test and signoff eCRF system	
	Study site staff training	
September 2015	Conduct site initiation visits at all sites	
	IMP delivery to all sites	
	First patient enrolled	
February 2016	Annual progress report to DMC, NIHR and MHRA	
July 2016	DMC and TSC meetings	
	Annual safety report to MHRA	
	Annual progress report to ethics	
January 2017	DMC and TSC meetings	
February 2017	Annual progress report to DMC, NIHR and MHRA	
April 2017	All sites end recruitment	
July 2017	DMC and TSC meetings	
	Annual safety report to MHRA	
	Annual progress report to ethics	
December 2017	Field-work (follow up) completed	
January 2018	Site close out visits	
	Database lock	
	Primary analysis begins	

May 2018	Analysis complete	
	HTA report submitted	
	Primary paper submitted for publication	

# 25. Learning lessons from the closure of the NEAT trial: qualitative follow-up

Difficulties recruiting to randomized controlled trials (RCTs) are common within medical research (Treweek et al., 2010; Watson & Torgerson, 2006) and have also been documented within addiction research (Ashery & McAuliffe, 1992; Demaret et al., 2014; Melberg & Humphreys, 2010; Oviedo-Joekes et al., 2015; Thomson et al., 2008). For example, a review of RCTs across a range of medical conditions found that nearly half received an extension due to recruitment problems (Sully et al., 2013). Addiction RCTs will encounter recruitment challenges similar to other medical RCTs (Thomson et al., 2008), but seem likely to face additional 'specific' difficulties. As various authors have already documented (Andreasson et al., 1990; Ashery & McAuliffe, 1992; Blanken et al., 2010; Oviedo-Joekes et al., 2015; Thomson et al., 2008), these potentially relate to:

- a) patient factors (e.g. barriers to attending appointments and services, lack of understanding about research, low motivation for treatment, concerns about being assigned to a placebo treatment, less patients in particular areas than expected, patient mobility creating difficulties contacting patients)
- service factors (e.g. very high staff workloads and limited clinic capacity, staff scepticism about new treatments, concerns about patients leaving successful treatments to participate in the RCT, limited research culture in the recruitment setting)

In consequence, it may be necessary to build a range of strategies into addiction RCT designs to facilitate and increase recruitment. These might, for example, include financial reimbursement/ incentives (Free et al., 2010; Martinson et al., 2000), simplified referral processes (Ashery & McAuliffe, 1992; Thomson et al., 2008), appointment reminders (Ashery & McAuliffe, 1992; Thomson et al., 2008), respondent-driven sampling, where trial recruits recruit further participants from their social networks (Burlew et al., 2011), and significant engagement with peer and community organisations (Burlew et al., 2011; Oviedo-Joekes et al., 2015; NIDA, 2008).

Ultimately, the successful execution of any individual RCT will depend on the characteristics of the study population, other setting and contextual factors, and the intervention being trialled. Nonetheless, the more we understand about the operationalization of trial designs within the addiction field, the more likely we are to complete studies successfully going forwards. In the UK, there is a notable lack

of methodological literature on the design and delivery of addiction-related RCTs, particularly those involving people with very complex drug problems. It is within this context that the Naltrexone Enhanced Addiction Treatment (NEAT) trial was conceived, designed and funded.

The NEAT trial was the result of an HTA-commissioned call to explore the potential clinical value of the new ultra-long-acting forms of naltrexone (implants and depot injections) versus existing oral naltrexone and also versus placebo (to test the ability to prevent relapse to heroin/opioid addiction). The study had the strongest trial design ever applied in the addictions field in the UK: a double-blind, double-dummy, placebo-controlled randomised clinical trial. The research team also had considerable experience of addictions research, including clinical trials. Despite this, there were problems executing the work. Initially, non-cooperation of the naltrexone manufacturer created time delays as a new supplier of both placebo and active implants had to be found. Next, there were organisational problems related to changes in the commissioning process for clinical services. Then, the two main trial sites (South London and Birmingham) failed to recruit participants, despite special attention and added resources.

Although a decision to wind down the NEAT trial was made in November 2016, ultra-long-acting naltrexone antagonist medications still need to be studied and they are therefore likely to be the subject of future NIHR/HTA trials. Before commissioning and undertaking any further research on naltrexone, or indeed further clinical research trials in this area, it is important to first learn lessons from the NEAT trial through some in-depth qualitative follow-up.

### 25.1 Aim

 To learn lessons from the NEAT trial in order to inform the design and conduct of a future successful naltrexone implant trial and to improve current understanding of conducting addiction treatment trials in clinical contexts.

### 25.2 Objectives

- To understand factors (patient, contextual and intervention related) that both facilitated and impeded the screening process of the NEAT trial
- To understand factors (patient, contextual and intervention related) that encouraged or discouraged patients from agreeing to participate in the NEAT trial
- To understand factors (patient, contextual and intervention related) that both facilitated and impeded progression from agreement to participate in the NEAT trial to actually joining the trial
- 4. To assess the treatment experiences of individuals who were accepted onto the NEAT trial but did not progress to join the trial

5. To assess the treatment experiences of all individuals who participated in the NEAT trial

- 6. To explore intended and unintended outcomes of participation in the NEAT trial
- 7. To ascertain the views and experiences of drug agency staff and research team members about the design and conduct of the NEAT trial
- 8. To ascertain the views of drug agency staff and research team members about how a future naltrexone trial should be designed and conducted
- 9. To assess whether the problems encountered were likely to be specific to naltrexone
- 10. To assess whether the problems encountered were likely to be specific to addiction trials

This follow-up has been designed to be incorporated into the NEAT trial over the period when it is being wound down. As a result, it is subject to a number of constraints. First, speed of data collection will be essential to ensuring that those involved in the NEAT trial can both be successfully located and recall sufficient information about the trial to enable meaningful analyses. Second, the small number of participants successfully recruited onto the trial (n=6) limits the scope of data collection. Third, time delays in securing NHS ethics approval could jeopardise the follow-up. For these practical reasons, it will be necessary to undertake a small exploratory follow-up study. Qualitative research, involving semi-structured interviews with a diverse range of individuals involved in the NEAT trial, provides an ideal method of generating the required data.

